TS-RT: Treated Set for Re-induction Treatment; TS-MT: Treated Set for Maintenance Treatment; NRI: No response imputation

Patients randomized to placebo in trial 1368-0005 who rolled-over to trial 1368-0017 and received re-induction treatment in trial 1368-0017, received in total 12 weeks of induction treatment with Spesolimab. Patients randomized to Spesolimab in trial 1368-0005 who rolled-over to trial 1368-0017 and received re-induction treatment in trial 1368-0017, received in total 24 weeks of induction treatment with Spesolimab. None of these patients achieved Clinical remission or Endoscopic improvement at week 12 and only few patients achieved Clinical response. Few patients who rolled-over from trial 1368-0005 to trial 1368-0017 and treated with maintenance treatment achieved Symptomatic remission.

Based on the results of the interim analyses of trials 1368-0005 and 1368-0017, the general benefit-risk assessment for patients currently treated in trial 1368-0017 cannot be evaluated. Therefore for these patients, the benefit-risk should be assessed by the investigator on an individual basis to evaluate patient continuation in the trial.

As recruitment of patients has been completed and no patients are ongoing in the preceding trials 1368-0004 and 1368-0005, no more patients can be enrolled in trial 1368-0017.

Summary of benefit-risk assessment

Due to the lack of mechanism- or compound-related safety signals as well as the antagonistic mode of action of BI 655130 (SPESOLIMAB) it is considered unlikely that UC patients be exposed to any undue risks in this trial. Considering the medical need of the development of an effective and well tolerated drug specifically and directly treating the structural aspects of UC, the benefit of this trial is considered to outweigh the potential risks for individual UC patients participating in this trial.

Based on the results of the above mentioned interim analysis of the preceding induction trial 1368-0005 and of trial 1368-0017, a benefit-risk assessment should be done by the investigator together on an individual basis to evaluate patient continuation in trial 1368-0017.

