2. TRIAL OBJECTIVES AND ENDPOINTS

2.1 MAIN OBJECTIVES, PRIMARY AND SECONDARY ENDPOINTS

Table 2.1:1 Definitions of Study Outcomes

Outcome	MCS subscore				Total MCS	Mod. MCS	Partial MCS	Additional Requirements
	RBS	mESS	SFS	PGA				
Clinical remission	0	≤ 1	0 or 1, if drop vs BL ¹ ≥ 1	-		≤ 2		
CS-free remission (in pts on CS at BL)	0	≤ 1	0 or 1, if drop vs BL ¹ ≥ 1	-		≤ 2		CS-free ≥ 12 wk and PMR for ≥ 12 wk
Clinical response	≤ 1 , or drop vs BL ¹ ≥ 1	Not missing	Not missing	Not missing	Drop vs BL ¹ ≥ 3 and $\geq 30\%$			
Partial MCS response	≤ 1 , or drop vs BL ¹ ≥ 1	-	Not missing	Not missing			$\downarrow \geq 2$ vs BL ¹	
Partial MCS remission	≤ 1	-	≤ 1	≤ 1			≤ 2	
Endoscopic remission	-	0	-	-				
Endoscopic improvement	-	≤ 1	-	-				
Complete remission	-	0	-	-				Robarts Histology Index (RHI) ≤ 6
Disease flare (after clinical response/remission, i.e. applicable on maintenance treatment only)	$\uparrow \geq 1$ vs BL ²	≥ 2 , AND $\uparrow \geq 1$ vs BL ²					$\uparrow \geq 2$ vs BL ²	pMCS \uparrow and RBS \uparrow from BL ² , conf. in 2 nd indep. Visit, with mESS \uparrow , and neg. enteric pathogens in stool

¹ BL of preceding induction study (1368-0005 Part 1)

² BL of current maintenance study (1368-0017)

Table 2.1:1 Definitions of Study Outcomes (cont.)

Outcome	Definition
Maintained remission	CR wk1+48, AND PMR at $\geq 75\%$ of intervening visits w/o flare
Durable remission	CR wk48, and PMR w/o flare in preceding 24 wks
Disease worsening	Worsening of clinical status or UC symptoms, in the investigator's opinion, requiring: 1) [during steroid taper] a suspension of tapering, or, a reversion of the steroid daily dose to the preceding daily dose, or, 2) treatment with rescue medication
Treatment Failure	Disease worsening, or a drug-related AE leading to discontinuation of study drug
Rescue Medication	New or dose increase of any non-study drug or surgical intervention for new or persist. symptoms of UC
Histological remission (HR)	Robarts Histology Index (RHI ≤ 6)

All criteria have to be met to qualify for the respective outcome at the same time

- Abbreviations: CR - clinical remission; pCR - partial clinical remission; CS - systemic corticosteroids; RBS – rectal bleeding score; mESS – modified endoscopic subscore; pts. - patients; RHI - Robarts Histology Index; SFS – stool frequency score; PGA – physician's global assessment; PMR - partial MCS remission; MCS – MayoScore; BL – baseline of previous parent induction trial

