## **5. ENDPOINTS**

For handling of missing data and the occurrence of inter-current events, unless otherwise specified, see [section 6.6](#).

Baseline for safety data, unless otherwise specified, is the last value prior to initiation of the re-induction treatment (for the re-induction period), or the maintenance treatment (for the pre-flare treatment period and post-flare treatment period), or the disease flare treatment (for the disease flare treatment period).

For the summary of all efficacy data, only those observations which were collected during the on-treatment period (i.e. first dose of spesolimab through to the last dose of spesolimab + 16 weeks) will be used.

Regarding the analyses of the change from baseline by visit for continuous efficacy endpoints, the baseline in current study is used, which refers to the last value prior to initiation of

- the re-induction therapy (i.e. baseline of re-induction period, denoted as R-baseline, corresponding to the week 12 assessment on the prior induction trial),
- or the maintenance therapy (i.e. baseline of the maintenance trial part, denoted as M-baseline, corresponding to the week 12 assessment on the prior induction/re-induction trial part).

For the specification of baseline definition for derivation of the applicable binary MCS endpoints, i.e. clinical response:

- the baseline is defined as the last non-missing value reported prior to the first dose of study drug on the preceding induction study, i.e., the definition of efficacy baseline from the parent trial.

However, for binary MCS endpoints after a disease flare treatment (specifically for disease flare treatment period), the baseline is defined as the last value prior to initiation of each disease flare treatment (i.e. baseline of disease flare treatment period, refers to data from flare confirmation visit with endoscopy or regular maintenance visit with endoscopy before administration of each disease flare treatment, denote as Fx-baseline, 'x' represents disease flare occurrence).

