### 6.6.2      **Efficacy endpoints**

**From CTP Section 7.5:** *With regards to the handling of missing data on those efficacy outcomes derived from the MCS, no missing data imputations are planned to be performed.*

In order to appropriately handle missing data in this trial, it is first necessary to define which are the inter-current events within each trial part, that lead to specific decisions being made upon the respective efficacy endpoint outcome, with such decisions being dependent upon the occurrence and timing of these events.

Any occurrence of the following will represent an inter-current event during both the re-induction and maintenance trial parts:

- Intake of rescue medication (as defined in [section 5.4.4](#)).  
Data after occurrence of such an event will be censored, and, handled subsequently according to the applicable missing data strategy described below.

In addition, any occurrence of the following will represent an inter-current event during the maintenance trial part:

- Occurrence of a confirmed disease flare (as defined in [Section 5.4.6](#)), or the intake of a dose of disease flare medication with 1200 mg BI 655130 SD.

Data after occurrence of such an event will be included in displays of the efficacy endpoints since treatment with spesolimab i.v. (to treat a disease flare) is not considered to represent a failed treatment outcome in this trial.

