			Window (per CTP)	Start (per CTP)	End (per CTP)	Start (extended)	End (extended)
V1	Screening/ M-baseline*	-7 to -2	n/a				
V1a	Screening	-2 to -1	n/a				
M1	M-Week 0	Day 1	+/-0	1 A	1 A	≤1 A	1 A
Planned On-Treatment Data							
M2	M-Week 12	Day 85	+/-7	78	92	2	127
M3	M-Week 24	Day 169	+/-7	162	176	128	211
M4	M-Week 36	Day 253	+/-7	246	260	212	295
...	...	...	...	Planned date-7	Planned date+7	End of extended window of last visit+1	Midpoint of planned days between current visit and next visit
M29/E OT	M-Week 336/EoT	Day 2353	+/-7	2346	2360	End of extended window of last visit+1	Minimum of (2395, LD B +112)
All Data (planned Off-Treatment data)							
Unsche duled	Unscheduled					2396	2444
EOS	EoS	Day 2466	+7	2466	2473	Minimum of (2396, LD B +113)	Day of last f-up value

Days are counted relative to the day of first s.c. treatment in maintenance period, which is defined as Day 1 for maintenance.

\* For derivation of binary MCS efficacy endpoints, the baseline refers to baseline of parent trial. The M-baseline for efficacy endpoint displays over time refers to EoT of parent trial (V1 of current study) for initial responders and visit I4 (RI-Week 12) for responders after re-induction.

A Note that measurements made at Day 1 and assigned to the on-treatment period (because mistakenly made after start of injection of trial treatment) via assessment on date and time (i.e. safety laboratory) will not be assigned to Day 1. Such data will be listed only.

B LD = Day of last treatment received in the overall maintenance treatment period regardless of flare occurrence;

Table 6.7: 3 Time windows for assignment of efficacy, safety lab, and vital signs to visits for statistical analysis for disease flare treatment period

Visit number/name	Visit label	Planned day	Time window (Days)				
			Window (per CTP)	Start (per CTP)	End (per CTP)	Start (extended)	End (extended)
F0y Fx-Week 0	Fx-baseline*	-5 to -3	n/a				
	Fx-Week 0	1	+/-0	1 A	1 A	≤1 A	1 A
Planned On-Treatment Data							
Fx-Week 6	Fx-Week 6	Day 43	+/-7	36	50	2	64
Fx-Week 12	Fx-Week 12	Day 85	+/-7	78	92	65	99

Visit number/name: 'x' represents disease flare occurrence.

Days are counted relative to the day of each corresponding flare i.v. treatment, which is defined as Day 1 of disease flare treatment period.

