\* For clinical response/remission assessment after disease flare treatment based on mayo score related calculation, the baseline refers to data from flare confirmation visit with endoscopy or regular maintenance visit with endoscopy before administration of each disease flare treatment.

A Note that measurements made at Day 1 and assigned to the on-treatment period (because mistakenly made after start of infusion of trial treatment) via assessment on date and time (i.e. safety laboratory) will not be assigned to Day 1. Such data will be listed only.

Repeated and unscheduled efficacy, safety and biomarker measurements will be handled similarly to scheduled measurements and will also be assigned to a time window depending upon the date of measurement.

Only one observation per time window will be selected for statistical analysis at a particular visit. Generally, the value which is closest to the protocol planned visit day will be selected. For composite endpoints based on MCS subscores, the date of PGA assessment will be used for time window assignment, and the PGA with the most complete components (RBS/SFS/mESS) at the same visit will be identified and then the closest will be selected. If the date of PGA assessment is missing, the date of endoscopy will be used instead for time window assignment and calculation of SFS and RBS, if available. If there are two observations which have the same difference in days to the planned day, the later value will be selected. If there are two observations on the same day, then [for vital signs per nominal time-point] the latest value (according to the date and time) will be selected, [for other endpoints] the worst value will be selected.

Assignment of efficacy observations to visits based on time windows will be based on the non-imputed (observed) data.

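### In the disease flare period the SAP measures clinical remission's stool-frequency drop from the flare visit instead of the parent-trial baseline, which can misclassify remission in both directions

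*SAP*

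**What the plan says.** Protocol Table 2.1:1 defines clinical remission by a rectal bleeding subscore (RBS) of 0, a modified endoscopic subscore (mESS) of at most 1, a modified Mayo score of at most 2, and an SFS condition, "0 or 1, if drop vs BL", where the drop must be at least 1. The table's first footnote identifies that baseline as "BL of preceding induction study (1368-0005 Part 1"). All criteria must be met together.

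SAP section 5 keeps the parent-trial baseline for binary Mayo endpoints in general, then makes an exception "for binary MCS endpoints after a disease flare treatment (specifically for disease flare treatment period"): the baseline becomes the last value before each flare treatment. The footnote to SAP Table 6.7: 3 names remission as well as response: "For clinical response/remission assessment after disease flare treatment based on mayo score related calculation, the baseline refers to data from flare confirmation visit", or to a regular maintenance visit with endoscopy before the infusion.

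For the overall maintenance period, the footnote to SAP Table 6.7: 2 says the opposite: "For derivation of binary MCS efficacy endpoints, the baseline refers to baseline of parent trial". That period keeps data collected after a flare (SAP 6.6.2): "Data after occurrence of such an event will be included in displays of the efficacy endpoints".

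The protocol's flare row, "Disease flare (after clinical response/remission, i.e. applicable on maintenance treatment only"), requires rises in RBS, mESS and partial Mayo score from the maintenance baseline. It sets no SFS condition.

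**The concern.** Clinical response measures change, so judging it from the flare visit is reasonable and is not questioned here. Remission is mainly a state. Its one baseline-dependent term asks whether an SFS of 1 is an improvement on the patient's original disease. Moving that term to the flare visit changes the question for a patient whose flare showed itself through bleeding, endoscopy and the physician's global assessment (PGA) while SFS stayed at 1. That patient can return to exactly the scores that counted as remission before the flare and still be tabulated as not in remission. A patient whose flare raised SFS can be credited with remission at an SFS no better than at parent-trial entry.

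The same week-12 assessment could then be remission in the overall maintenance display and non-remission in the flare display. SAP section 4, which lists changes to the planned analysis, mentions only the relabelling of patient sets. At stake is the interpretation of a small descriptive count of remissions after flare treatment.

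**Working it through.** The plan states no figure to reproduce, so the check applies the rules to scores.

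**Rules (protocol Table 2.1:1; integer subscores 0 to 3 assumed)**
- Remission: RBS = 0; mESS ≤ 1; SFS = 0, or SFS = 1 with (baseline SFS − 1) ≥ 1; RBS + mESS + SFS ≤ 2.
- Flare, against the maintenance baseline: RBS up ≥ 1; mESS ≥ 2 and up ≥ 1; partial Mayo (RBS + SFS + PGA) up ≥ 2. RBS +1 and PGA +1 meet the last condition with SFS unchanged.

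**Where the baselines disagree.** SFS 0 meets the condition on either baseline and SFS 2 or 3 fails on either, so only a week-12 SFS of 1 matters. Among the 4 × 4 = 16 pairs of parent and flare SFS, with the other remission criteria met:
- parent 2–3, flare 0–1: remission on the parent baseline only, 2 × 2 = 4 pairs;
- parent 0–1, flare 2–3: remission on the flare baseline only, 2 × 2 = 4 pairs;
- the remaining 16 − 4 − 4 = 8 pairs agree.

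**Worked cases** (order: RBS, mESS, SFS, PGA)

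| Case | Parent | Maintenance start | Flare | Week 12 | Parent baseline | Flare baseline |
|---|---|---|---|---|---|---|
| A | 2,2,3,2 | 0,1,1,0 | 2,2,1,1 | 0,1,1,0 | SFS 3−1=2: remission | 1−1=0: not |
| B | 2,3,2,3 | 0,1,1,1 | 1,2,1,2 | 0,0,1,0 | 2−1=1: remission | 1−1=0: not |
| C | 2,3,1,2 | 0,1,1,0 | 2,2,2,2 | 0,1,1,0 | 1−1=0: not | 2−1=1: remission |

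Each case is a clinical response at maintenance start (total Mayo 9 to 2, 10 to 3 and 8 to 2). Each meets the flare rule (RBS +2, +1, +2; mESS 2 and +1 in all three; partial Mayo +3, +2, +5). In A the week-12 scores equal the pre-flare remission scores. In B the week-12 endoscopy is normal and there is no bleeding.

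**Enumeration.** Of all maintenance/flare score combinations, 4,040 meet the flare definition. None has RBS 0 or mESS ≤ 1, so a patient meeting the current definition cannot be in remission at the flare visit. In 510, SFS is unchanged at 0 or 1; 255 of these are at SFS 1, where the loss can arise. Restricting to patients in parent-baseline remission at maintenance start who later regain those scores, remission is lost in all 232 combinations with SFS 1 before and at the flare and in all 152 with SFS 1 before and 0 at the flare. It is lost in none where pre-flare SFS was 0 or flare SFS was 2 or 3. These are counts of score patterns, not patient frequencies.

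**Scale.** Remission is rare in this programme. Protocol Table 1.4:2 shows 0 + 0 + 2 + 2 = 4 of 90 at week 12 of the parent trial. Table 1.4:5 shows none among 10 + 16 + 14 + 10 = 50 after re-induction: "None of these patients achieved Clinical remission or Endoscopic improvement at week 12". The number of flare-treated patients is not given. If it were 13 to 24 (an assumption), one reclassified patient would move the rate by 100/13 = 7.7 to 100/24 = 4.2 points.

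**The case against.** - **The affected table is not visible.** The flare-period endpoint definitions (SAP 5.4 and 7.6) and the SAP's own remission definition (Table 9.1.1: 1) are not in the supplied text, and section 5 introduces the binary-endpoint baseline with clinical response as its instance. This limits certainty. The Table 6.7: 3 footnote nevertheless names remission, and if an unseen section keeps the parent baseline, the footnote contradicts it and needs correcting anyway.
- **The choice may be deliberate.** One baseline for response and remission is tidy in a table about the effect of one infusion. It also guards against crediting an infusion that changed nothing. For a flare meeting the current definition that guard is unnecessary: RBS is at least 1 and mESS at least 2 at the flare visit, so reaching remission means improving on both.
- **Not every flare-treated patient meets that definition.** This part stands. SAF-FT includes anyone given one flare infusion, and deviation F1.02 (infusion without sufficient evidence of a flare) leads to no exclusion. With parent SFS 3, and RBS 0, mESS 1, SFS 1 both at infusion and at week 12, the parent baseline gives remission (3 − 1 = 2) with no change, while the flare baseline does not (1 − 1 = 0). Before Global Amendment 4 the flare definition had no bleeding criterion, so those patients may have improved on endoscopy alone.
- **Fractional scores.** SFS and RBS are three-day averages and no rounding rule is visible, so confining the disagreement to an SFS of exactly 1 depends on the integer assumption.

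A reader might infer that the flare-period remission rate is biased downwards. The documents do not support that: the patterns split 4 and 4, and their frequency among patients is unknown. Nor does the remark in Global Amendment 4 that more than half of the first 24 responders relapsed or flared give a count of flare-treated patients. It combines relapse with flare and predates the current flare definition.

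**Conclusion.** The concern holds as a minor inconsistency. On the visible text, SAP section 5 and the Table 6.7: 3 footnote measure remission's SFS drop from the flare visit, while protocol Table 2.1:1 and the SAP's overall maintenance period use the parent-trial baseline. At a week-12 SFS of 1 this can both remove and add remissions. The net direction and the number of patients affected cannot be determined from the documents; because remission is rare, a single patient could matter to the count.

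One might also infer that week-336 remission, the primary endpoint or treatment decisions are affected. They are not. Week-336 remission belongs to the overall maintenance period and keeps the parent baseline, and the primary endpoint concerns adverse events. The stopping rule in protocol 3.3.4.1 judges response against the original induction baseline and accepts protocol-defined remission as the alternative. Only the descriptive flare-period display is touched.

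The conclusion assumes integer subscores, and that the SAP sections not supplied repeat the protocol's remission criteria without exempting the SFS term.

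**What to change.** Keep the flare-visit baseline for clinical response in the disease flare treatment period. Add one sentence to SAP section 5 stating that, for clinical remission in that period, the SFS drop is measured from the parent-trial baseline as in protocol Table 2.1:1, and remove remission from the Table 6.7: 3 footnote.

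To cover infusions given without sufficient evidence of a flare, flag patients already in parent-baseline remission at the flare visit and do not count them as regained remissions. The flag will not pick out flares under the pre-Amendment 4 definition that had no bleeding. Those patients had mESS of at least 2, so remission still means endoscopic improvement; a table note is enough.

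The cost is one sentence, one footnote edit and one derived flag. No new data or tables are needed.

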Footnotes for all Flow Charts:

1. Visit V1 of this long-term extension study should be performed during the last visit (V6/EOT) of the preceding trial 1368-0005 Part 1 or 1368-0004. Assessments performed at last visit (V6/EOT) in the previous trial do not have to be repeated at visit 1 in this trial. Patients not eligible to take part in trial 1368-0017 shall complete follow-up visit 16 weeks after last dose given in trial 1368-0004 or 1368-0005 Part I.
2. Visit V1a can be performed via telephone. Main reason for this visit is to check eligibility based on sigmoidoscopy and patient diary results in order to plan the next visit.
3. Sigmoidoscopies have to be performed every 48 weeks during maintenance treatment period. Additional sigmoidoscopies are to be done: a) at screening (EOT of previous trial); b) at W12 of re-induction period to check response to i.v. re-induction ([Flowchart 2](#)); c) In case of disease flare, an unscheduled confirmatory sigmoidoscopy has to be performed, followed in 12 weeks after i.v. re-induction to check response to disease flare treatment. Two sets of mucosal biopsies will be taken; 1 set for gene expression analyses and 1 set for histopathology/IHC analyses at each visit indicated. Sigmoidoscopy images will be centrally read by an external independent assessor(s); management of images will be performed by an external vendor. Colonoscopy instead of sigmoidoscopy can be performed if required as colon cancer screening per local guidelines.
4. Physical examination: C=complete, T=targeted. Refer to [Section 5.2.1](#) and [5.2.2](#). Measurement of vital signs should precede blood sampling and be assessed pre-dose at all dosing visits and at screening. In addition, at visits with s.c. study drug administration, vital signs will be assessed at approx. 10 minutes after study drug administration. At visits with i.v. study drug administration, vital signs will be assessed at approximately 5 and 60 minutes after study drug administration. Monitor for signs and symptoms of hypersensitivity reactions for 1h following i.v. study drug administration.

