- Total MCS is calculated as the sum of RBS, mESS, SFS and PGA
- Modified MCS is calculated as the sum of RBS, mESS and SFS
- Partial MCS is calculated as the sum of RBS, SFS and PGA

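### SAP 6.7 counts endoscopy data when choosing records for partial Mayo endpoints, so an off-plan flare or post-flare visit can displace a closer scheduled visit

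*SAP*

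**What the plan says.** The default in SAP 6.7 is proximity: "Generally, the value which is closest to the protocol planned visit day will be selected". Mayo composites get their own rule. First, "For composite endpoints based on MCS subscores, the date of PGA assessment will be used for time window assignment". Then, among the candidate records, "the PGA with the most complete components (RBS/SFS/mESS) at the same visit will be identified and then the closest will be selected". The visible text makes no exception for composites that omit mESS.

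Unscheduled records compete for the same window: "Repeated and unscheduled efficacy, safety and biomarker measurements will be handled similarly to scheduled measurements". In SAP Table 6.7: 2 a maintenance window ends at the "Midpoint of planned days between current visit and next visit". SAP 6.6.2 keeps data collected after a flare in the efficacy displays.

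In the protocol, the notes to Table 2.1:1 state: "Partial MCS is calculated as the sum of RBS, SFS and PGA". The table sets no mESS condition for partial MCS response or partial MCS remission (PMR). On endoscopy, flow chart footnote 3 says: "Sigmoidoscopies have to be performed every 48 weeks during maintenance treatment period". It adds: "In case of disease flare, an unscheduled confirmatory sigmoidoscopy has to be performed", with a further endoscopy 12 weeks after the i.v. dose.

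**The concern.** A component that the endpoint never uses helps decide which record is analysed. At a 12-weekly visit without endoscopy, a record with full diary data holds two of the three listed components. A flare-confirmation visit with full diary data, or the 12-week post-flare endoscopy visit, holds three. Completeness is applied before distance, so the endoscopy visit wins however much further it lies from the planned day, provided it is in the window.

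This affects only patients who had an extra endoscopy, that is, patients who flared, so it is not random noise across the cohort. What is at stake is whether a by-visit partial Mayo result labelled M-Week 24 describes the patient near week 24 or at a flare-related visit some weeks away.

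**Working it through.** **1. Reproduce the windows (SAP Table 6.7: 2).** Planned day = 7 × week + 1, so weeks 12, 24, 36, 48 and 336 fall on Days 85, 169, 253, 337 and 2353. Window ends are the midpoints of adjacent planned days:
- M2: (85 + 169)/2 = 127
- M3: (169 + 253)/2 = 211
- M4: (253 + 337)/2 = 295
- M29: 2353 + 42 = 2395

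All four match the table.

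**2. Windows without a planned endoscopy.** There are 336/12 = 28 maintenance windows. Endoscopy every 48 weeks covers weeks 48, 96, 144, 192, 240, 288 and 336, which is 7. The other 28 − 7 = 21 (75%) have none on the original schedule.

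**3. Largest distance from plan.** The M3 window runs from Day 128 to Day 211, so a record can lie 169 − 128 = 41 days before plan or 211 − 169 = 42 days after. M2 runs from Day 2 to Day 127: 85 − 2 = 83 days before or 127 − 85 = 42 after.

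**4. Apply the rule in the M3 window (planned Day 169).** The count is of RBS, SFS and mESS; every record has a PGA.

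| Records in the window | Count | SAP rule picks | Counting RBS and SFS only picks |
|---|---|---|---|
| A. Scheduled Day 169, no endoscopy; flare visit Day 205, complete | 2 v 3 | Day 205 | Day 169 |
| B. As A, flare visit lacks one diary item | 2 v 2 | Day 169 | Day 169 |
| C. As A, flare visit lacks both diary items | 2 v 1 | Day 169 | Day 169 |
| D. As A, scheduled visit also has complete endoscopy data | 3 v 3 | Day 169 | Day 169 |
| E. Flare endoscopy done at the regular visit | one record | that visit | that visit |
| F. Post-flare visits on Days 158 (no endoscopy) and 200 (complete) | 2 v 3 | Day 200 | Day 158 |

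In A the chosen record is 205 − 169 = 36 days off plan, against 0.

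Case F assumes a flare infusion on Day 116. The 6-week visit is then Day 116 + 42 = 158 and the 12-week endoscopy Day 116 + 84 = 200. The distances are 169 − 158 = 11 and 200 − 169 = 31 days. F also assumes that PGA and diary data are collected at the 6-week visit.

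**5. What a swap does to one patient's result.** PMR needs RBS, SFS and PGA each ≤ 1 and partial MCS ≤ 2. A flare needs RBS up by ≥ 1 and partial MCS up by ≥ 2 from the maintenance baseline. Take whole-number subscores with PMR at that baseline. Of the 260 baseline/flare combinations that meet both flare conditions, 2 are still in PMR at the flare visit. This is an unweighted count, not a frequency. It shows that in case A, if the Day 169 visit was in PMR, the binary result would usually change. In case F the later visit may be better or worse than the earlier one, so the direction is open.

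**The case against.** **Another reading of the rule.** If the reference to the same visit means that records are ranked only within one visit, before the closest visit is chosen, nothing is replaced. The more natural reading is that the components must come from the same visit as the PGA. The alternative cannot be excluded, but two programmers could then build different datasets from one sentence, which is itself a reason to clarify it.

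**No affected table is visible.** The one secondary endpoint, clinical remission at week 336, needs mESS, and for it the rule is sensible. The primary endpoint does not use the rule. The SAP sections on further endpoints are not in the available text, so a separate rule for partial MCS may exist there. This stands as a limit on the point.

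**Flares already count elsewhere.** By their definitions in Protocol Table 2.1:1, maintained and durable remission fail on a flare in the relevant period, whichever record fills the window. Steroid-free remission requires 12 weeks of PMR, which a true flare in that time should break. The first part stands in full. The second narrows the exposure, but the definition has no explicit flare term, so the PMR element still depends on which record is picked.

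**Replacement is conditional.** A reader might infer that a flare visit always replaces the scheduled one in any window. Cases B to E show otherwise. Protocol 3.1 allows a flare to be observed at a regular visit. Protocol 7.3.2 sets diary scores to missing on bowel-preparation days, the endoscopy day and the day after. Against that, Protocol 3.1 starts diary entry as soon as a flare is suspected, and the flare definition needs the partial score, so complete flare records should be common.

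**Consequences are limited.** All analyses are descriptive, individual values are listed, flares are tabulated by 12-week interval, and patients with more than one confirmed flare are withdrawn from treatment. This stands.

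**Conclusion.** The point holds for partial MCS response and remission. As written, the rule can replace a closer record with a complete, off-plan flare or post-flare endoscopy visit in maintenance windows where the closer record lacks complete endoscopy data. That is possible in 21 of 28 windows on the original schedule. The displacement is up to 42 days, or 83 days before plan in the M2 window. The exposure is by-visit partial MCS results and the PMR element of steroid-free remission, all descriptive.

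This rests on three assumptions: completeness is ranked across all records in the window, the further-endpoint sections hold no separate rule, and partial MCS is summarised by these windows.

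Two stronger inferences are not supported. One is that results are pulled uniformly toward each patient's worst moment; the post-flare endoscopy is chosen by the same mechanism and can move results either way. The other is a frequency taken from the rationale for Global Amendment 4, where more than 50% of the first 24 responders relapsed or flared within 6 months: at least 13 patients, or 13/48 = 27% of their week-12 and week-24 windows. That experience arose under the earlier q12w regimen and flare definition. The calculation also assumes an off-plan, complete endoscopy record for every event and includes windows where plain closeness would pick the same record. The documents do not allow the number of changed windows to be computed.

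**What to change.** In SAP 6.7, judge completeness only over the components the endpoint uses, then select the record closest to the planned day:
- partial MCS endpoints: RBS, SFS, PGA
- modified MCS and clinical remission: RBS, SFS, mESS
- total MCS and clinical response: all four

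The same sentence should say whether completeness is compared across all records in the window or only within a visit. If the further-endpoint sections already hold a rule for partial MCS, a cross-reference is enough.

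The cost is one sentence and a per-endpoint selection flag in the analysis dataset, with no new data. The small downside is that different Mayo endpoints may draw on different records within one window, which a table footnote can state.
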